### 6.3. Follow-up visits

Gastroparesis Registry 2 follow-up visits will be scheduled every 24 weeks after enrollment. Participants will return for follow-up visits at 24, 48, 72, 96, 120, 144, 168, 192, 216, and 240 weeks after enrollment. Each visit will have an interval of time (follow-up visit window) surrounding the ideal target date for the visit during which the study procedures may be completed and the data may be keyed in the study database. The ideal target date for a follow-up visit is the exact anniversary (24, 48, 72, 96, 120, 144, 168, 192, 216, 240 weeks) from enrollment. Visit windows will be constructed to be contiguous, so that at any point in time, a follow-up visit window is open. The specific procedures to be completed at each of the follow-up visits are detailed in the Data Collection Schedule in the Appendix ([section 11.2](#)).

#### *Weeks 24, 72, 120, 168 and 216 visits*

Follow-up medical history (medication changes/additions, symptom exacerbations or interventions, surgeries, hospital admissions, new diagnoses of co-morbidities, complications of interventions such as infections), and physical examination including weight, height, and waist/hip circumference, blood pressure, heart rate, respiratory rate and body temperature. Blood will be drawn to obtain HbA1c values for patients with diabetes. Participants will complete the following questionnaires:

- Patient Assessment of Upper Gastrointestinal Disorders Symptom Severity Index (PAGI-SYM)
- Patient Assessment of Upper Gastrointestinal Disorders - Quality of Life (PAGI-QOL)
- Beck Depression Inventory (BDI-II)
- State Trait Anxiety Inventory (STAI)
- Neuropathy Total Symptom Score (NTSS-6)
- Nausea Profile and Vomiting questionnaire
- Patient Health Questionnaire (PHQ-15)

#### *Week 48 visits (2 separate days)*

The week 48 follow-up visits require 2 separate days of testing and participants will come fasting for each day of testing. Medications that delay gastric emptying such as narcotic analgesics and medications that enhance gastric emptying such as prokinetics will be stopped for 3 days prior to the visits. A follow-up medical history (medication changes/additions, symptom exacerbations or interventions, surgeries, hospital admissions, new diagnoses of co-morbidities, complications of

interventions such as infections, documentation of any additional GI tests performed as part of standard of care), and physical examination, including weight, height, and waist/hip circumference, blood pressure, heart rate, respiratory rate and body temperature will be performed.

Participants will have a repeat 4 hour gastric emptying scintigraphy test of solids only using the Egg Beaters® with toast and jam will be performed. Medications taken during the past week will be recorded. For diabetic patients, a fasting blood glucose level must be checked within the hour prior to the gastric emptying test to ensure it is less than 270 mg/dL. Patients will also complete the PGI-SYM questionnaire immediately prior to the gastric emptying test.

On a second day, the autonomic function testing and a repeat EGG with water load test will be performed. On the morning of the EGG and water load satiety test, the patient will arrive fasting. Patients may take their usual medications with a small amount of water (up to 4 oz) up to two hours prior to the study, but should refrain from coffee, tea, or juice. After arriving to the clinic, the patient's blood glucose level must be checked to ensure it is less than 270 mg/dL. If the patient's blood glucose level is greater than 270 mg/dL the EGG and water load satiety test must be rescheduled for another day.

Draw 10 mL of blood for serum banking and 10 mL of blood for plasma banking at the NIDDK Biosample Repository. Blood will be drawn to obtain HbA1c values for patients with diabetes. Participants will complete the following additional questionnaires:

- Patient Assessment of Upper Gastrointestinal Disorders - Quality of Life (PAGI-QOL)
- Beck Depression Inventory (BDI-II)
- State Trait Anxiety Inventory (STAI)
- Neuropathy Total Symptom Score (NTSS-6)
- Block 2005 Food Frequency Questionnaire
- Block Energy Expenditure Survey
- Rome III Diagnostic Questionnaire for Adult Functional GI Disorders
- Health related quality of life (SF-36v2)
- Patient Health Questionnaire (PHQ-15)
- Nausea Profile and Vomiting questionnaire
- Brief Pain Inventory
- GpCRC abdominal pain questionnaire

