**Screening visit 2:** Patients must discontinue use of proton pump inhibitors for 7 days, and stop histamine 2 antagonists, prokinetics, narcotics, anticholinergics, and cannabinoids for 3 days prior to this visit. If the patient normally takes insulin, they will be asked to take only half of their normal long-acting insulin. Record fasting glucose for diabetic patients; the blood glucose level must be checked to ensure it is less than 270 mg/dL to continue with the test. Patients will come to the center after fasting and will have a baseline electrogastrogram (EGG). Then they will eat a nutrient bar (SmartBar®) with water and swallow a wireless motility capsule (SmartPill®) with additional water, followed by a 90 minute EGG recording. Patients will continue to abstain from prokinetics, proton pump inhibitors, 'over the counter' laxatives, isotonic PEG electrolyte preparations (e.g. MiraLax), and prescription laxatives (e.g. lubiprostone) after ingesting the SmartPill® until they return for the follow-up visit in 4-7 days. These tests are described in detail in section [6.7.3](#). (All details of the EGG recording procedure, wireless motility capsule test, and specific questionnaires will be in the Standard Operating Procedures (SOP) manual.)

**Screening visit 3 (4-7 days after visit 2):** Record fasting glucose for diabetic patients; the blood glucose level must be checked to ensure it is less than 270 mg/dL to continue with the test. If the patient's blood glucose level is greater than 270 mg/dL, the EGG and water load test must be rescheduled for another day.

The study physician or coordinator will collect the SmartPill® receiver and download the data, and then the patient will undergo autonomic function testing to evaluate heart rate variability (see section [6.7.4](#)). Next the patient will have a 15 minute baseline electrogastrogram (EGG) and then complete a water load test, followed by a 30 minute EGG recording (this test is described in section [6.7.5](#)). Patients will have blood drawn for DNA and serum/plasma banking as the last procedure for the visit.

**Enrollment:** The GpR 2 data system will include software to check patient eligibility based on keyed

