### 6.7.3. Wireless motility capsule and EGG

A wireless motility capsule, SmartPill® measures gastric emptying, small bowel transit time (SBTT), and colon transit time (CTT) and is approved for the evaluation of presumed gastroparesis and slow transit constipation. The SmartPill® has pH, pressure, and temperature sensors to quantify gastric, small bowel, and colon transit and contractility. SmartPill® showed good correlation with gastric scintigraphy (R=0.73) in 87 controls and 61 patients with prior gastroparesis diagnoses.

SmartPill® sensitivities and specificities (65% and 87%) were comparable or superior to 4 hour scintigraphy (44% and 93%) and supported equivalency of SmartPill® with scintigraphy methods advocated by consensus guidelines. In constipated patients, SmartPill® colon transits showed good correlations with radioopaque marker studies. In retrospective analyses, SmartPill® testing gave many new diagnoses in 86 patients with symptoms in the upper or lower gut including detecting slow transit constipation or small bowel dysmotility in patients thought to have only gastroparesis. This emphasizes the effectiveness of SmartPill® to characterize regional and generalized motor disorders in one test.

*Test procedure criteria:* Patients must be able to stop proton pump inhibitors for 7 days, and stop histamine 2 antagonists, prokinetics, narcotics, anticholinergics, and cannabinoids for 3 days. The SmartPill® is contraindicated in patients with bezoars (retained liquid or poorly organized solids are permitted), dysphagia, prior gut lumen surgery (prior Nissen fundoplication is permitted), known strictures, prior inflammatory bowel disease, prior diverticulitis, chronic frequent NSAID use, and cardiac medical devices (gastric stimulators, insulin pumps, continuous glucose monitors are permitted).

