***Patient preparation required for the SmartPill® with EGG test***

- 1) Patient will stop proton pump inhibitors for 7 days prior to visit 2;
- 2) Patient will stop histamine 2 antagonists, prokinetics, narcotics, anticholinergics, constipation medications (over the counter laxatives, isotonic polyethylene glycol (PEG) electrolyte preparations (e.g. MiraLax), and prescription laxatives (e.g. lubiprostone), and cannabinoids for 3 days prior to the visit; and
- 3) Patients will continue to abstain from prokinetics, proton pump inhibitors, and ‘over the counter’ laxatives, isotonic PEG electrolyte preparations (e.g. MiraLax), and prescription laxatives (e.g. lubiprostone) after ingesting the SmartPill® until they return for the follow-up visit in 4-7 days.
- 4) Patients will not swallow the SmartPill®, if they have a history of bezoars (retained liquid or poorly organized solids are permitted), significant dysphagia, prior gut lumen surgery (except fundoplication), known strictures, prior inflammatory bowel disease, and cardiac medical devices (gastric stimulators, insulin pumps, continuous glucose monitors are permitted).

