#### *Test protocol*

On the morning of the EGG and water load satiety test, the patient will arrive fasting. Patients may take their usual medications with a small amount of water (up to 4 oz) up to two hours prior to the study, but should refrain from coffee, tea, or juice. After arriving to the clinic, the patient's blood glucose level must be checked to ensure it is less than 270 mg/dL. If the patient's blood glucose level is greater than 270 mg/dL the EGG and water load satiety test must be rescheduled for another day.

Baseline symptoms prior to EGG recording will be obtained using visual analog scales for stomach fullness, hunger, nausea, bloating, and abdominal discomfort. The subject will mark each symptom line with a vertical line to indicate how they currently feel in terms of that symptom. Once the EGG and respiratory signals are stable, the baseline EGG recording period can begin. Patients will undergo a 15 minute baseline EGG in a reclining chair with the subject positioned at a 30-45 degree tilt.

Patients will begin the Water Load Satiety Test. For this, participants will sit upright. During the test, participants will drink cool water for a 5 minute period until they feel "**completely full.**" The total volume of water consumed will be recorded.

A continuous 30 minute EGG recording is then obtained. The patient's symptoms are recorded using VAS at 10, 20, and 30 minutes after ingestion of the water (at the end of the 0-10 minute, 11-20 minute, and the 21-30 minute post-satiety periods). The test is completed after the 30 minute recording period and the electrodes are removed. (Complete details will be contained in the SOP.)

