**Stopping medications for gastroparesis:** For participation in this study, prescribed medications may need to be stopped temporarily for the testing required for the study: gastric emptying tests, wireless motility capsule, and electrogastronomy. These medications include those that speed up stomach emptying. Medicines like this include metoclopramide (Reglan), erythromycin, and domperidone (Motilium). Medications that slow down the movement through the GI tract include anticholinergic agents such as Levsin and NuLev and pain medications such as Percocet, Tylenol #3, Vicodan, Dilaudid, Fentanyl patch, and others. If patients are taking any of these medications and they are helping their symptoms, if they are stopped, their symptoms may return or worsen. The stopping of medications is for a short time only (1 week) and is not felt to cause any undue hardship on the patient.

**Safety issues related to patient privacy:** There is a potential risk to patient privacy. Every effort will be made to maintain patient's privacy. It is the investigator's responsibility to conduct the protocol under the current version of Declaration of Helsinki, Good Clinical Practice, and rules of local IRBs. The investigator must ensure that the patient's anonymity is maintained in their data submission to the Scientific Data Research Center. Patients will be identified only by an identification code but not by their name, SSN, or hospital medical record number. Investigators will maintain a separate confidential enrollment log which matches identifying codes with the patients' names and addresses (i.e., available only to local clinic staff). All study material will be maintained in strict confidence.

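### Medication rules for the EGG/water-load test conflict within both baseline and week 48; separately, the stated one-week drug stop is shorter than the schedule gives, and the two capsule contraindication lists differ

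*Protocol*

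**What the plan says.** **Week 48 (section 6.3).** The visit takes two separate days: scintigraphy on one, autonomic testing and the repeat EGG/water-load test on the other. The opening paragraph covers narcotic analgesics and similar drugs that delay emptying, and adds that "medications that enhance gastric emptying such as prokinetics will be stopped for 3 days prior to the visits". For the second day the text then states: "Patients may take their usual medications with a small amount of water (up to 4 oz) up to two hours prior to the study".

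**Baseline (section 6.2).** Before screening visit 2 (solid-meal EGG and capsule), PPIs are stopped for 7 days. H2 antagonists, prokinetics, narcotics, anticholinergics and cannabinoids are stopped for 3 days. After the capsule, "Patients will continue to abstain from prokinetics, proton pump inhibitors" and laxatives until the return visit 4-7 days later; section 6.7.3 repeats this. That return visit is screening visit 3, where the baseline EGG/water-load test is done. Section 6.2 refers to section 6.7.5 for the procedure, and 6.7.5 reads: "Patients may take their usual medications with a small amount of water (up to 4 oz) up to two hours prior to the" study.

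**Risk section (9.1).** Drugs may be stopped for gastric emptying, capsule and EGG testing. "The stopping of medications is for a short time only (1 week") is the stated duration, and the section concludes from it that there is no undue hardship.

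**Capsule contraindications (section 6.7.3).** The test procedure criteria include "prior diverticulitis, chronic frequent NSAID use, and cardiac medical devices". Item 4 of the patient preparation list has instead "known strictures, prior inflammatory bowel disease, and cardiac medical devices".

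**The concern.** A patient whose usual drugs include a prokinetic cannot follow both instructions at either time point. The same holds for a narcotic at week 48. A site has to choose, and the protocol gives no rule for choosing.

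The results feed stated aims. The secondary objectives in section 3 compare the EGG and symptom response to the water load with the response to the solid meal, and relate water-load EGG to gastric emptying results. Solid-meal EGG and scintigraphy are done after defined drug stops; the water-load test has no settled condition. The test is also scheduled at screening and at week 48 (section 11.2), so anyone analysing change over 48 weeks inherits the ambiguity.

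Two side issues concern participants rather than estimates. Section 9.1 rests its hardship judgement on a duration that the schedule can exceed, while itself warning that symptoms may return or worsen. And a site using only the preparation list could give the capsule to a patient whom the test procedure criteria exclude.

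**Working it through.** **1. The two EGG/water-load days side by side**

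| | Stop or abstain text | Permission text |
|---|---|---|
| Screening visit 3 | Prokinetics, PPIs, laxatives withheld until this visit (6.2, 6.7.3) | Usual drugs up to 2 hours before (6.7.5) |
| Week 48, day 2 | Drugs that delay or enhance emptying stopped 3 days before both days (6.3) | Usual drugs up to 2 hours before (6.3, 6.7.5) |

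The permission is the same in both rows, so the contradiction lies within each time point.

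**2. What each reading implies for drug status**

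- *Permission governs both days.* The rule is the same at baseline and week 48. But the water-load EGG is done on usual drugs, while the solid-meal EGG and scintigraphy it is compared with are done after stops.
- *Stop text governs both days.* Prokinetics are withheld at both. PPIs and laxatives are withheld at baseline but not named at week 48. Narcotics are named at week 48 but have no stated continuation from visit 2 to visit 3.
- *Stop text at baseline, permission at week 48.* Prokinetics, PPIs and laxatives are off at baseline and may be on at week 48.
- *Permission at baseline, stop text at week 48.* Prokinetics and narcotics may be on at baseline and are off at week 48.

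Drug status can therefore differ in either direction, or not at all. The protocol gives no proportion of patients on each class and no drug effect on EGG or water volume, so no bias can be computed.

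**3. Length of the stop**

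Inputs: days off before visit 2, from 6.2 (PPIs 7, prokinetics 3) and 6.7.3 (laxatives 3); gap from visit 2 to visit 3, 4-7 days, from 6.2; stated duration, 1 week = 7 days, from 9.1.

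Days off by visit 3 = days before visit 2 + gap.

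- PPIs: 7 + 4 = 11 to 7 + 7 = 14 days, which exceeds the stated 7 by 4 to 7 days.
- Prokinetics and laxatives: 3 + 4 = 7 to 3 + 7 = 10 days, which exceeds it by 0 to 3 days.
- H2 antagonists, narcotics, anticholinergics, cannabinoids: 3 days before visit 2, no stated continuation.

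The stated week is reproduced only by the shortest prokinetic or laxative case.

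**4. Capsule lists**

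Prior diverticulitis and chronic frequent NSAID use are in the test procedure criteria but not in preparation item 4. Dysphagia without qualification in the first becomes significant dysphagia in the second.

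**The case against.** The best defence is that the passages can be read together: the permission could cover only drugs not otherwise stopped, and the SOP, which is not available here, may say so. That is possible, but neither 6.3 nor 6.7.5 makes the exception, and the operative text should not depend on it.

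A reader might infer that the 48-week change in EGG or water volume is confounded. The documents do not support that. The permission is identical at both time points, so if sites follow it the rule matches. No stated objective or hypothesis concerns that change, and Table 6 lists no EGG or water-load outcome. Only a risk remains.

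A reader might also infer that the one-week stop is too short and should be lengthened. Nothing in the protocol shows that, and it is a clinical question. What stands is that the description is shorter than the schedule. Even this has limits: 9.1 names prokinetics, anticholinergics and pain drugs but not PPIs, which come in only through its general reference to prescribed drugs stopped for capsule testing. For narcotics and anticholinergics one week does not understate the stop before visit 2.

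Nor can it be said that participants are told the wrong duration, because the consent text is not available.

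Drug use is partly recorded: past-week medications are captured with scintigraphy. But baseline scintigraphy may predate registration by up to 6 months, and at week 48 it is on a different day from the EGG, so neither record is tied to the EGG/water-load day. Covariate adjustment does belong to each paper's own statistical plan, but such a plan needs the data.

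On the capsule, the fuller list comes first, and passing the shorter one does not waive it. The capsule is given at baseline only, so this has no bearing on change in EGG. The lists still differ.

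**Conclusion.** The instructions for the EGG/water-load test are contradictory at baseline and again at week 48. The consequence is a risk of non-comparable drug status between sites, between time points, and between the water-load EGG and the solid-meal EGG and scintigraphy. The size of any bias cannot be derived from the protocol, and there would be none from the rule over time if every site applied the permission at both visits.

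Separately, the one-week description in 9.1 is 4-7 days shorter than the scheduled PPI stop and 0-3 days shorter than the prokinetic and laxative stop. This assumes that abstention runs without a break from before visit 2 to visit 3, as 6.2 and 6.7.3 state, and, for PPIs, that 9.1 is meant to cover every drug stopped for the capsule test. Also separately, the two capsule lists disagree on three items. All of this should be corrected. None of it establishes that a result is biased or that any particular medication rule is wrong.

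**What to change.** 1. Reconcile sections 6.2, 6.3, 6.7.3 and 6.7.5 into one medication condition, stated in the same words for screening visit 3 and the week-48 EGG/water-load day. The clinical team chooses the condition.
2. Record medication status on both EGG/water-load days. Require proposals that use these data to account for it where status differs between visits or between the tests compared.
3. Restate the duration in 9.1, by drug class, to match the reconciled schedule, and check the consent against it.
4. Reconcile the two capsule contraindication lists after clinical review.

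The cost is protocol wording, a site memo, a medication entry on the EGG day form, and a consent change only if the check finds a mismatch. No visit or procedure is added. For patients already tested, sites could be asked which instruction they followed, so that existing data can be classified.

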#### ***Weeks 96, 144, 192, and 240 visits***

Follow-up medical history (medication changes/additions, symptom exacerbations or interventions, surgeries, hospital admissions, new diagnoses of co-morbidities, complications of interventions such as infections), and physical examination including weight, height, and waist/hip circumference, blood pressure, heart rate, respiratory rate and body temperature. Draw 10 mL of blood for serum banking and 10 mL of blood for plasma banking at the NIDDK Biosample Repository. Blood will be drawn to obtain HbA1c values for patients with diabetes. Participants will complete the following questionnaires:

- PAGI-SYM, PAGI-QoL
- Beck Depression Inventory (BDI-II)
- State Trait Anxiety Inventory (STAI)
- Rome III functional GI disorders questionnaire
- Health related quality of life (SF-36v2)

- Patient Health Questionnaire (PHQ-15)
- Block Energy Expenditure Survey
- Block 2005 Food Frequency Questionnaire
- Nausea Profile and vomiting questionnaire
- Brief Pain Inventory
- GpCRC abdominal pain questionnaire

### *Interim visits*

Separate entries will be made in the Gastroparesis Registry 2 data system for symptom flares requiring medical intervention. In addition, information will be obtained each time a new medicine for gastroparesis symptoms is started and the response to this treatment.

#### **6.4. Data form contents**

The Gastroparesis Registry 2 data collection forms will capture the following:

- Demographics
- Onset and duration of symptoms
- Nature and severity of symptoms
- Characteristics of nausea and vomiting
- Prior gastrointestinal and gynecologic surgeries and the dates of these surgeries
- Characteristics of weight prior to and since onset of gastroparesis symptoms
- Other GI symptoms particularly chronic pancreatitis
- Presence of diabetes (including gestational diabetes)
- If diabetic, onset, type, glycemic control, other system involvement (eye, kidney, heart, peripheral and autonomic neuropathy)
- Presence of “overlap” symptoms
- Results from upper GI endoscopy performed within 2 years prior to registration
- Results from gastric emptying test including PAGA-SYM and fasting glucose on day of gastric emptying test for diabetic patients performed at a GpCRC clinical center within 6 months prior to registration
- Other medical problems particularly any history of connective tissue disorder
- Family history of GI or related illness
- Past medical/surgical events and illness history, including coronary artery disease or stroke

**Baseline medication history:** The GpR 2 data forms will capture all prescription medications taken within 6 months prior to registration. These will include medications taken for the treatment of gastroparesis, pain (visceral or somatic) and many others. GpR 2 data forms will also include information on use of alternative therapies, antioxidants, vitamins, and/or other dietary supplements. Any known medication allergies will be documented.

**Follow-up medical history:** Follow-up health history will include data on symptom severity; nutritional changes, medication changes or additions; key events or interventions; surgeries; hospital admissions; new diagnoses of co-morbidities; complications of diabetes such as retinopathy, neuropathy, nephropathy; and cardiovascular events.

